**IMPORTANT NOTE:**

If you accidentally select the wrong IRB type or “Protocol Process Type” while your Initial Review (IR) application is in draft form (unsubmitted), you may change your selections. Please contact the Office of Research Integrity (ORI) at [contact], [[contact]](mailto:[contact]), or [request a consult](#) to resolve any questions regarding your selections *prior* to submitting your Initial Review application.

If your submitted IR application has been returned to you for requested revisions or additional information, to streamline the review process **do not make changes** to your selections here unless instructed to do so by the ORI/IRB.

Changes to this section cannot be made after initial approval has been issued (the option is not available for MR or CR).

For guidance, see:

- [Which IRB should review my research?](#)
- [Which Protocol Process Type?](#)
- ["Getting Started"](#)

**Which IRB**

Medical  NonMedical

**Protocol Process Type**

Exemption  
 Expedited (Must be risk level 1)  
 Full

The revised Common Rule expanded exemption certification category 4 for certain secondary research with identifiable information or biospecimens. The regulations no longer require the information or biospecimens to be existing. For more information see the [Exemption Categories Tool](#).

**To Be Completed Only If Protocol is to Receive Expedited Review****Applicability**

- A. Research activities that (1) present no more than \*minimal risk to human subjects, and (2) involve only procedures listed in one or more of the following categories, may be reviewed by the IRB through the expedited review procedure authorized by 45 CFR 46.110 and 21 CFR 56.110. The activities listed should not be deemed to be of minimal risk simply because they are included on this list. Inclusion on this list merely means that the activity is eligible for review through the expedited review procedure when the specific circumstances of the proposed research involve no more than minimal risk to human subjects.
- B. The categories in this list apply regardless of the age of subjects, except as noted.
- C. The expedited review procedure may not be used where identification of the subjects and/or their responses would reasonably place them at risk of criminal or civil liability or be damaging to the subjects' financial standing, employability, insurability, reputation, or be stigmatizing, unless reasonable and appropriate protections will be implemented so that risks related to invasion of privacy and breach of confidentiality are no greater than minimal.
- D. The expedited review procedure may not be used for classified research involving human subjects.
- E. IRBs are reminded that the standard requirements for informed consent (or its waiver, alteration, or exception) apply regardless of the type of review—expedited or convened—utilized by the IRB.

*\*“Minimal risk” means that the probability and magnitude of harm or discomfort anticipated in the research are not greater in and of themselves from those ordinarily encountered in daily life or during the performance of routine physical or psychological examination or tests. 45 CFR 46.102(i)*

Check the appropriate categories that apply to your research project:

Study was originally approved by the full IRB at a convened meeting.

1) Clinical studies of drugs and medical devices only when condition (a) or (b) is met.

- A. Research on drugs for which an investigational new drug application is not required. (Note: Research on marketed drugs that significantly increases the risks or decreases the acceptability of the risks associated with the use of the product is not eligible for expedited review.)
- B. Research on medical devices for which (i) an investigational device exemption application is not required\*; or (ii) the medical device is cleared/approved for marketing and the medical device is being used in accordance with its cleared/approved labeling.\*\*

\* Study must meet one of the IDE Exempt categories listed on the Device Form Attachment.

\*\* An approved Device used in research according to its approved labeling is considered Exempt from IDE requirements.

NOTE: Select Category 1 for compassionate use medical device applications or individual patient expanded access investigational drug applications for which FDA has waived the requirement for full review.

2) Collection of blood samples by finger stick, heel stick, ear stick, or venipuncture as follows:

- A. From healthy, nonpregnant adults who weigh at least 110 pounds. For these subjects, the amounts drawn may not exceed 550 ml in an 8 week period and collection may not occur more frequently than 2 times per week; or
- B. From other adults and children\* considering the age, weight, and health of the subjects, the collection procedure, the amount of blood to be collected, and the frequency with which it will be collected. For these subjects, the amount drawn may not exceed the lesser of 50 ml or 3 ml per kg in an 8 week period and collection may not occur more frequently than 2 times per week.

NOTE: Intravenous (IV), Port, Central, or any other lines are NOT eligible under this category even if the research involves “minimal risk”.

\*In Kentucky, “child/children” refers to all individuals less than 18 years of age unless the individual(s) is/are legally emancipated. (See [Informed Consent SOP](#) for discussion of “Emancipated Individuals” under Kentucky state law.) Individuals less than 18 years of age who are not emancipated meet the federal definition for “child” (e.g., DHHS, FDA, and U.S. Department of Education). Children are defined in the HHS regulations as “persons who have not attained the legal age for consent to treatments or procedures involved in the research, under the applicable law of the jurisdiction in which the research will be conducted.” If conducting research outside the state of Kentucky, you are responsible for complying with applicable state law.

3) Prospective collection of biological specimens for research purposes by noninvasive means. Examples:

- A. Hair and nail clippings in a nondisrupting manner;
- B. Deciduous teeth at time of exfoliation or if routine patient care indicates a need for extraction;
- C. Permanent teeth if routine patient care indicates a need for extraction;
- D. Excreta and external secretions (including sweat);
- E. Uncannulated saliva collected either in an unstimulated fashion or stimulated by chewing gumbase or wax or by applying a dilute citric solution to the tongue;
- F. placenta removed at delivery;
- G. Amniotic fluid obtained at the time of rupture of the membrane prior to or during labor;
- H. Supra- and subgingival dental plaque and calculus, provided the collection procedure is not more invasive than routine prophylactic scaling of the teeth and the process is accomplished in accordance with accepted prophylactic techniques;
- I. Mucosal and skin cells collected by buccal scraping or swab, skin swab, or mouth washings;
- J. Sputum collected after saline mist nebulization.

4) Collection of data through noninvasive procedures (not involving general anesthesia or sedation) routinely employed in clinical practice, excluding procedures involving x-rays or microwaves. Where medical devices are employed, they must be cleared/approved for marketing. (Studies intended to evaluate the safety and effectiveness of the medical device are not generally eligible for expedited review, including studies of cleared medical devices for new indications.) Examples:

- A. Physical sensors that are applied either to the surface of the body or at a distance and do not involve input of significant amounts of energy into the subject or an invasion of the subject's privacy;
- B. Weighing or testing sensory acuity;
- C. Magnetic resonance imaging;
- D. electrocardiography, electroencephalography, thermography, detection of naturally occurring radioactivity, electroretinography, ultrasound, diagnostic infrared imaging, doppler blood flow, and echocardiography;
- E. moderate exercise, muscular strength testing, body composition assessment, and flexibility testing where appropriate given the age, weight, and health of the individual.

5) Research involving materials (data, documents, records, or specimens) that have been or will be collected solely for non-research purposes (such as medical treatment or diagnosis) as well as research involving existing information or specimens that were previously collected for research purposes, provided they were not collected for the currently proposed research. (Note: Some research in this category may qualify for Exempt review. This listing refers only to research that is not exempt.)

(Note: If submission includes materials previously collected for either non-research or research purposes in a protocol for which IRB approval expired, you may check Category 5. However, a separate category must also be selected for prospective collection of data/specimens obtained solely for research purposes)

6) Collection of data from voice, video, digital, or image recordings made for research purposes.

7) Research on individual or group characteristics or behavior (including, but not limited to, research on perception, cognition, motivation, identity, language, communication, cultural beliefs or practices, and social behavior) or research employing survey, interview, oral history, focus group, program evaluation, human factors evaluation, or quality assurance methodologies. (Note: Some research in this category may be exempt from the HHS regulations for the protection of human subjects. This listing refers only to research that is not exempt.)

\*\*\* If this modification changes the scope of your activities to include COVID-19 related research, please insert "COVID19" at the start of your Project and Short Titles.\*\*\*

Select One:

- This modification does not increase risk to study participants.
- This modification may or will increase risk to study participants.

Is this modification request due to an Unanticipated Problem/Adverse Event, or Protocol Violation?

- Yes
- No

In your professional opinion, does this modification involve information that might relate to a subject's willingness to continue to take part in the research?

- Yes
- No

If yes, state how the information will be communicated to subjects (i.e., re-consent, send letter, etc.):

**For each proposed modification, include a justification.**

Example: [name], is being added as co-investigator because she has expertise with the subjects on this protocol. She has completed human subject protections training, and is authorized to obtain consent.

Principal Investigator has been changed to [name].

Title of Project: (Use the exact title listed in the grant/contract application, if applicable).

If your research investigates any aspect of COVID-19, please include "COVID19" at the beginning of your Project Title and Short Title

Tracking and Reducing Alcohol Consumption for Adolescent and Young Adult Survivors of Cancer

**Short Title Description**

Please use a few key words to easily identify your study - this text will be displayed in the Dashboard listing for your study.

TRAC-AYA

Anticipated Ending Date of Research Project: 6/30/2025

Maximum number of human subjects (or records/specimens to be reviewed) 94

After approval, will the study be open to enrollment of new subjects or new data/specimen collection? 1  Yes  No

Are you requesting that the UK IRB serve as the lead IRB for a multi-site study, **OR** that the UK IRB defer review to another IRB? [Click [here](#) for "IRB Reliance" help]

Yes  No

If "Yes," before completing your IRB application, fill out the [Reliance Request Form](#) and submit it to [[contact]](mailto:[contact]).

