**Study Population:**

Describe the characteristics of the subject population, including age range, gender, ethnic background and health status. Identify the criteria for inclusion and exclusion.

Provide the following information:

- A description of the subject selection criteria and rationale for selection in terms of the scientific objectives and proposed study design;
- A compelling rationale for proposed exclusion of any sex/gender or racial/ethnic group;
- Justification for the inclusion of vulnerable groups such as children, prisoners, adults with impaired consent capacity, or others who may be vulnerable to coercion or undue influence.

Please consider this [FDA Guidance on Enrollment of Participants from Underrepresented Populations in Clinical Studies](#)

**Key Informant Interviews:** Participants (n=14) will consist of AYA cancer survivors (n=6), Oncology providers (n=3) including physicians, nurses, nurse practitioners, or physician's assistants, psycho-oncology providers (n=3) (i.e. mental health professionals treating AYA cancer patients), and community advocates (n=2) (i.e. partners from the KY Cancer Consortium and the KY American Cancer Society). Survivors must be between the ages of 18-39 who were diagnosed with cancer between the ages of 15-39. Oncology providers must have been in practice for at least 6 months and spend at least 25% of their practice with AYA cancer patients. Psycho-Oncology providers must have been in practice for at least 6 months and see AYA cancer patients. All participants must speak English.

**Open Pilot:** Participants (n=4) will consist of AYA cancer survivors. To be eligible to participate in the open pilot, survivors must meet the following criteria:

- 1) diagnosed with cancer between age 15-39;
- 2) currently age 18-39;
- 3) 1-10 years posttreatment (hormonal therapy allowed);
- 4) report unhealthy alcohol use in the previous 3 months, defined as:
  - a. exceeding moderate daily drinking levels (more than 1 drink/day for women, more than 2 drinks/day for men) at least 3 times in the past 3 months OR
  - b. engaging in heavy weekly drinking (more than 7 drinks/week for women, more than 14 drinks/week for men) at least once in the past 3 months OR
  - c. engaging in binge drinking (more than 3 drinks/sitting for women, more than 4 drinks/sitting for men) at least once in the past 3 months;

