- 5) meeting hazardous drinking criteria on the AUDIT-C questionnaire, defined as a score of 3 or higher for women/4 or higher for men (The AUDIT-C consists of items 1, 2, and 3 from the full AUDIT questionnaire);

Participants with severe psychopathology (psychosis, suicidal behavior, substance dependence) will be excluded from the study. The AUDIT questionnaire will be administered as part of screening to determine alcohol dependence; if survivors have a score of 20 or higher, they will be referred to UKMCC Social Work.

**RCT:** n=50, Intervention group (TRAC) n=25, and Control group (education and monitoring) n= 25. To be eligible to participate in the RCT, survivors must meet the following criteria:

- 1) diagnosed with cancer between age 15-39;
- 2) currently age 18-39;
- 3) 3 months - 15 years posttreatment (hormonal therapy allowed);
- 4) report unhealthy alcohol use in the previous 3 months, defined as:
  - a. exceeding moderate daily drinking levels (more than 1 drink/day for women, more than 2 drinks/day for men) at least 3 times in the past 3 months OR
  - b. engaging in heavy weekly drinking (more than 7 drinks/week for women, more than 14 drinks/week for men) at least once in the past 3 months OR
  - c. engaging in binge drinking (more than 3 drinks/sitting for women, more than 4 drinks/sitting for men) at least once in the past 3 months; OR
- 5) meeting hazardous drinking criteria on the AUDIT-C questionnaire, defined as a score of 3 or higher for women/4 or higher for men (The AUDIT-C consists of items 1, 2, and 3 from the full AUDIT questionnaire)
- 5) Reside in the United States

Just as with the Open Pilot, participants with severe psychopathology will be excluded from the study. The AUDIT questionnaire will be administered as part of screening to determine alcohol dependence; if survivors have a score of 20 or higher, they will be referred to UKMCC Social Work (if a patient at UK HealthCare). Non-UK patients will be provided with information for SAMHSA's treatment finder, national helpline, and local resources based on the zip code provided at the time of screening. Survivors who score a 20 or higher on the AUDIT questionnaire will not be eligible for the study, as this study is not designed to manage alcohol dependence and its immediate health risks.

Enrollment will begin February 2022 and continue through May 2023 or until the proposed participant pool is reached.

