**Impact:** This study proposes an innovative intervention to address a prevalent, but unaddressed health problem in rural AYA survivors. The intervention is informed by preliminary data, leverages the high digital health literacy of AYAs, and will overcome access barriers to increase reach. At the end of this study, we will have feasibility data to inform a definitive RCT of TRAC-AYA to test efficacy, which we will test in the Markey Cancer Center Affiliate Network, a network of rural cancer clinics in Kentucky. If successful, TRAC-AYA could address alcohol use in the over 2 million AYAs living in the US and be generalized to other survivor populations, thus having a high impact on survivorship health outcomes and post-treatment care.

Added June 2023: We will further adapt and refine the TRAC intervention to suit an older population of cancer survivors through semi-structured interviews with key informants (N=35 cancer survivors aged 40 or older).

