#### Added June 2023: Study Procedures: Key Informant Interviews

We will conduct key informant interviews with 35 adult cancer survivors. These interviews will be conducted in person, via phone, or video conference, with no follow-ups or re-contacts. We will collect phone numbers or emails to provide \$40 Amazon e-gift card as compensation. Prior to the interview, all participants will be emailed a copy of the consent form (PDF) and a link to an online REDCap consent form. If they are recruited or are conducting their interview in person, we will provide a paper copy. The interviewer will discuss this consent form with the participants, answer any questions that they have, and ensure that the participant signs the consent form electronically prior to beginning the interview. Participants will also complete a brief demographics survey, either before or directly after the interview.

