**RCT Enrollment:** The RCT will enroll 50 participants, 25 per condition. First, we will administer a screener to verify participants meet all inclusion criteria. If patients do not wish to be screened and are not interested in participating in the study, we will ask that they complete a brief Refusal to Screen Questionnaire to indicate why and collect basic demographic information to inform generalizability of the obtained sample. If participants complete the screener and indicate that they are interested in learning more about the study, we will collect their contact information and a member of the study team will follow-up with the participant to obtain informed consent and complete enrollment if they meet all eligibility criteria. Pre-screened participants who screen eligible and indicate interest in the study will be automatically directed to the approved eConsent in REDCap. If participants are determined to be eligible for the study and

consent to enroll, we will also collect information for at least 1 emergency contact (participants have the option to provide a backup emergency contact). We will contact these individuals only in cases of extreme distress, adverse events, or threats of self-harm. We will make clear to participants that we will not specify the nature of the research study to these individuals. If the participant is a patient at UK HealthCare, researchers will also contact their medical care team should any of these cases arise. Once participants have been enrolled in the study they will complete a baseline questionnaire, which may be done in-person, online via REDCap, via phone, or via mail per participant preference. It will ask about 1) Alcohol use, consequences, and attitudes, 2) Tobacco and other substance use, 3) Cancer history, 4) Overall physical/mental health, 5) Healthcare usage and history, 6) Financial toxicity, 7) Health literacy, 8) Coping Self-efficacy, 9) Social support, and 10) Drinking refusal self-efficacy.

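### The figures for study size do not agree: a stated maximum of 94 subjects, cohorts that sum to 103, and an RCT of 50 in the protocol but 40 in the SAP.

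*Combined protocol and SAP*

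**What the plan says.** The Short Title Description of the application sets "Maximum number of human subjects (or records/specimens to be reviewed) 94".

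The cohorts are described elsewhere in the same application:

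- **Key informant interviews, Aim 1 (Study Population):** 14 people, made up of 6 survivors, 3 oncology providers, 3 psycho-oncology providers and 2 community advocates.
- **Open pilot (Study Population):** "Participants (n=4) will consist of AYA cancer survivors".
- **RCT (Study Population):** "n=50, Intervention group (TRAC) n=25, and Control group (education and monitoring) n= 25". Data Collection & Research Materials repeats it: "The RCT will enroll 50 participants, 25 per condition".
- **Interviews added in June 2023:** the Objectives give "N=35 cancer survivors aged 40 or older", and the added Study Procedures section says "We will conduct key informant interviews with 35 adult cancer survivors".

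The planned-enrollment table has entries for Asian, Black/African American, Latinx and White participants, split by sex. The American Indian/Alaskan Native row holds zeros, and the remaining rows are blank.

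SAP 1.2 bases the sample size on 40. SAP 1.3 gives Aim 1 as 18 and Aim 2 as 40. The Informed Consent Process section says that the study no longer enrolls and that no consenting is under way.

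**The concern.** A maximum number of subjects should be at least the sum of the cohorts that the same application plans to enroll. Here it is smaller. If every cohort filled as described, the study would pass its stated number. If the maximum were respected, at least one cohort would fall short of its target.

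The total also depends on the size of the RCT, for which the documents hold two values. The maximum itself enters no analysis. The RCT size does: the feasibility counts in SAP 1.2 are written for 40 people, while the protocol randomizes 50. A reader cannot tell which denominator the decisions on a future efficacy trial will use.

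**Working it through.** **Stated figure.** 94 (Short Title Description).

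**Sum of the cohorts.**

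- Key informants: 6 + 3 + 3 + 2 = 14
- With the RCT at 50 (protocol): 14 + 4 + 50 + 35 = 103
- With the RCT at 40 (SAP): 14 + 4 + 40 + 35 = 93
- Without the interviews added in June 2023: 68 (RCT of 50) or 58 (RCT of 40)

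None of these equals 94. With the protocol's RCT size the gap is 103 − 94 = 9.

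**Planned-enrollment table (men + women).**

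- Asian: 4 + 2 = 6
- Black/African American: 6 + 8 = 14
- Latinx: 5 + 4 = 9
- White: 25 + 49 = 74

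If all rows are mutually exclusive: 6 + 14 + 9 + 74 = 103. If Latinx is an ethnicity that overlaps the race rows: 6 + 14 + 74 = 94. The two readings differ by exactly the Latinx row, and each agrees with one of the conflicting totals. The application does not say which reading was meant.

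**Who would absorb the gap.** If the other three cohorts filled, the RCT would have 94 − (14 + 4 + 35) = 41 of 50 places. If the RCT and the Aim 1 cohorts filled, the later interviews would have 94 − (14 + 4 + 50) = 26 of 35. Other splits of the 9 are possible. The Study Population section plans enrollment from February 2022 to May 2023, and the older-survivor interviews were added in June 2023, so the second split is at least as plausible as the first.

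**What the RCT size touches in the SAP.** SAP 1.2 ties three statements to 40: the number approached to recruit 40, the number retained out of 40, and the power for adherence of 0.72 against 0.50. At n = 40 and a true probability of 0.60:

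- The negative binomial probability of having to approach 55 or more people is 0.978. The SAP says it is below 0.05.
- The binomial probability of 19 or fewer retained is 0.074, and of 18 or fewer 0.039. The SAP says that the probability for 19 or fewer is below 0.05.
- The adherence power is 0.79 (exact) or 0.82 (normal approximation), consistent with the SAP's 80%. At n = 50 it would be 0.86 or 0.90.

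The first two results are a separate matter from the count. They do mean that these figures need recomputing, not just scaling from 40 to 50.

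**The case against.** The strongest reply is that this is a form field with no statistical role, in a study that has stopped enrolling. It appears in no hypothesis or analysis, and the maximum can no longer cut any cohort. That stands, and it makes the point minor.

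A second reply is that the table supports 94. On one reading it does, and on the other it supports 103. A reader might take the table as independent confirmation of 103. The documents do not support that, because the total depends on how the Latinx row was meant.

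A reader might also infer that the maximum leaves the RCT only 41 of its 50 places. That holds only if the other three cohorts fill first, which no section says. The same arithmetic gives 26 of 35 later interviews with the RCT intact.

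Overlap between cohorts could in principle close the gap, but nine people would have to count twice. No overlap is described: interviews are said to involve no re-contact, SAP 1.3 counts Aim 1 as 18 (14 + 4), and the added interviews require age 40 or over while the RCT requires 18 to 39. The field label also admits records, but adding screened records would raise the required number and widen the gap.

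Finally, the conflict between 40 and 50 stands apart from the maximum. It belongs here because the total cannot be settled without it.

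**Conclusion.** The inconsistency is real and small. The described cohorts exceed the stated maximum by 9 people with the RCT at 50, and fall 1 short of it with the RCT at 40. This rests on two assumptions: that the four cohorts are different people, and that the field counts people. The closeness of 93 to 94 may suggest a maximum that was not updated when the RCT figure became 50. That is only an inference, since 93 is not 94 and one reading of the table gives 94 exactly.

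A reader might infer that the study enrolled more people than its stated maximum. The documents do not report actual enrollment, so an overrun can be neither asserted nor excluded.

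The part with statistical content is the RCT size. SAP 1.2 and 1.3 use 40 where the protocol consistently gives 50.

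**What to change.** 1. Reconcile the maximum with the cohort totals and with the number actually enrolled in each cohort. If all four cohorts stand as described, the total is 103. Report whether 94 was exceeded.
2. State whether the Latinx row of the planned-enrollment table is separate from the race rows or overlaps them.
3. Use one RCT size throughout. Restate SAP 1.2 and 1.3 for the RCT size actually used, and recompute the enrollment, retention and adherence figures for it.

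The cost is one figure and a clarifying line in an IRB modification, plus a short recalculation in two SAP sections. No new data are needed.
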